#### **8.4.5.2. Exposure During Breastfeeding**

An EDB occurs if:

- A female participant is found to be breastfeeding while receiving or after discontinuing study intervention.
- A female nonparticipant is found to be breastfeeding while being exposed or having been exposed to study intervention (ie, environmental exposure). An example of environmental EDB is a female family member or healthcare provider who reports that she is breastfeeding after having been exposed to the study intervention by ingestion, inhalation, or skin contact.

The investigator must report EDB to Pfizer Safety within 24 hours of the investigator's awareness, irrespective of whether an SAE has occurred. The information must be reported using the CT SAE Report Form. When EDB occurs in the setting of environmental exposure, the exposure information does not pertain to the participant enrolled in the study, so the information is not recorded on a CRF. However, a copy of the completed CT SAE Report Form is maintained in the investigator site file.

An EDB report is not created when a Pfizer drug specifically approved for use in breastfeeding women (eg, vitamins) is administered in accordance with authorized use. However, if the infant experiences an SAE associated with such a drug, the SAE is reported together with the EDB.

#### **8.4.5.3. Occupational Exposure**

The investigator must report any instance of occupational exposure to Pfizer Safety within 24 hours of the investigator's awareness using the CT SAE Report Form regardless of whether there is an associated SAE. Since the information about the occupational exposure does not pertain to a participant enrolled in the study, the information is not recorded on a CRF; however, a copy of the completed CT SAE Report Form must be maintained in the investigator site file.

#### **8.4.6. Cardiovascular and Death Events**

Not applicable.

#### **8.4.7. Disease-Related Events and/or Disease-Related Outcomes Not Qualifying as AEs or SAEs**

Not applicable.

#### **8.4.8. Adverse Events of Special Interest**

Not applicable.

#### **8.4.8.1. Lack of Efficacy**

This section is not applicable because efficacy is not expected in the study population.

#### **8.4.9. Medical Device Deficiencies**

Not applicable.

##### **8.4.9.1. Time Period for Detecting Medical Device Deficiencies**

Not applicable.

##### **8.4.9.2. Follow-Up of Medical Device Deficiencies**

Not applicable.

##### **8.4.9.3. Prompt Reporting of Device Deficiencies to the Sponsor**

Not applicable.

##### **8.4.9.4. Regulatory Reporting Requirements for Device Deficiencies**

Not applicable.

#### **8.4.10. Medication Errors**

Medication errors may result from the administration or consumption of the study intervention by the wrong participant, or at the wrong time, or at the wrong dosage strength.

Medication errors are recorded and reported as follows:

Recorded on the Medication Error Page of the CRF	Recorded on the Adverse Event Page of the CRF	Reported on the CT SAE Report Form to Pfizer Safety Within 24 Hours of Awareness
All (regardless of whether associated with an AE)	Any AE or SAE associated with the medication error	Only if associated with an SAE

Medication errors include:

- Medication errors involving participant exposure to the study intervention;
- Potential medication errors or uses outside of what is foreseen in the protocol that do or do not involve the study participant.

Such medication errors occurring to a study participant are to be captured on the medication error page of the CRF, which is a specific version of the AE page.

Whether or not the medication error is accompanied by an AE, as determined by the investigator, the medication error is recorded on the medication error page of the CRF and, if applicable, any associated AE(s), serious and nonserious, are recorded on the AE page of the CRF.

In the event of a medication dosing error, the sponsor should be notified within 24 hours.

Medication errors should be reported to Pfizer Safety within 24 hours on a CT SAE Report Form **only when associated with an SAE**.

## 8.5. Pharmacokinetics

### 8.5.1. Plasma for Analysis of Nirmatrelvir and Ritonavir

Blood samples of approximately 4 mL, to provide approximately 1.5 mL plasma, will be collected for measurement of plasma concentrations of nirmatrelvir and ritonavir as specified in the **SoA**. Instructions for the collection and handling of biological samples will be provided in the laboratory manual or by the sponsor. The actual date and time (24-hour clock time) of each sample will be recorded.

The actual times may change, but the number of samples will remain the same. All efforts will be made to obtain the samples at the exact nominal time relative to dosing. Collection of samples up to and including 10 hours after dose administration that are obtained within 10% of the nominal time relative to dosing (eg, within 6 minutes of a 60-minute sample) will not be captured as a protocol deviation, as long as the exact time of the collection is noted on the source document and the CRF. Collection of samples more than 10 hours after dose administration that are obtained  $\leq$ 1 hour away from the nominal time relative to dosing will not be captured as a protocol deviation, as long as the exact time of the collection is noted on the source document and the CRF.

CCI

Genetic analyses will not be performed on these plasma samples unless consent for this was included in the informed consent. Participant confidentiality will be maintained.

CCI

[figure not shown]
[figure not shown]
[figure not shown]

The PK samples must be processed and shipped as indicated in the instructions provided to the investigator site to maintain sample integrity. Any deviations from the PK sample handling procedure (eg, sample collection and processing steps, interim storage or shipping conditions), including any actions taken, must be documented and reported to the sponsor.

On a case-by-case basis, the sponsor may make a determination as to whether sample integrity has been compromised.

Any changes in the timing or addition of time points for any planned study assessments must be documented and approved by the relevant study team member and then archived in the sponsor and site study files, but will not constitute a protocol amendment. The IRB/EC will be informed of any safety issues that require alteration of the safety monitoring scheme or amendment of the ICD.

CCI

CCI

## **8.6. Genetics**

### **8.6.1. Specified Genetics**

Specified genetic analyses are not evaluated in this study.

### **8.6.2. Retained Research Samples for Genetics**

A 4-mL blood sample optimized for DNA isolation Prep D1 will be collected according to the [SoA](#), as local regulations and IRBs/ECs allow.

Retained Research Samples may be used for research related to the study intervention(s). Genes and other analytes (eg, proteins, RNA, nondrug metabolites) may be studied using the retained samples.

See [Appendix 5](#) for information regarding genetic research. Details on processes for collection and shipment of these samples can be found in the laboratory manual and supporting documentation.

## **8.7. Biomarkers**

Biomarkers are not evaluated in this study.

### **8.7.1. Specified Gene Expression (RNA) Research**

Specified gene expression (RNA) research is not included in this study.

### **8.7.2. Specified Protein Research**

Specified protein research is not included in this study.

### **8.7.3. Specified Metabolomic Research**

Specified metabolomic research is not included in this study.

### **8.7.4. Retained Research Samples for Biomarkers**

These Retained Research Samples will be collected in this study:

- 10 mL whole blood (Prep B2 optimized for serum).

Retained Research Samples will be collected as local regulations and IRB/ECs allow according to the [SoA](#).

Retained Research Samples may be used for research related to the study intervention(s). Genes and other analytes (eg, proteins, RNA, nondrug metabolites) may be studied using the retained samples.

See [Appendix 5](#) for information regarding genetic research. Details on processes for collection and shipment of these samples can be found in the laboratory manual and supporting documentation.

### **8.8. Immunogenicity Assessments**

Immunogenicity assessments are not included in this study.

### **8.9. Health Economics**

Health economics/medical resource utilization and health economics parameters are not evaluated in this study.

CCI

## **9. STATISTICAL CONSIDERATIONS**

Detailed methodology for summary and statistical analyses of the data collected in this study is outlined here and further detailed in the SAP, which will be maintained by the sponsor. The SAP may modify what is outlined in the protocol where appropriate; however, any major modifications of the primary endpoint definitions or their analyses will also be reflected in a protocol amendment.

## 9.1. Statistical Hypotheses

There are no statistical hypotheses for this study.

## 9.2. Analysis Sets

For purposes of analysis, the following analysis sets are defined:

Participant Analysis Set	Description
Enrolled	"Enrolled" means a participant's, or their legally authorized representative's, agreement to participate in a clinical study following completion of the informed consent process and randomization. A participant will be considered enrolled if the informed consent is not withdrawn prior to participating in any study activity after screening. Potential participants who are screened for the purpose of determining eligibility for the study, but do not participate in the study, are not considered enrolled, unless otherwise specified by the protocol.
Safety analysis set	All participants who take at least 1 dose of study intervention. Participants will be analyzed according to the product they actually received.
PK concentration set	All participants who take at least 1 dose of study intervention and in whom at least 1 plasma concentration value is reported.
PK parameter set	All participants who take at least 1 dose of study intervention and in whom at least 1 of the plasma PK parameters of primary interest are reported.

## 9.3. Statistical Analyses

The SAP will be developed and finalized before any analyses are performed and will describe the analyses and procedures for accounting for missing, unused, and spurious data. This section is a summary of the planned statistical analyses of the primary and secondary endpoints.

### 9.3.1. Pharmacokinetic Analyses

#### 9.3.1.1. Derivation of Pharmacokinetic Parameters

Plasma PK parameters of nirmatrelvir and ritonavir will be derived (as data permits) from the concentration-time data using standard noncompartmental methods as outlined in [Table 2](#). Actual PK sampling times will be used in the derivation of PK parameters. In the case that actual PK sampling times are not available, nominal PK sampling time will be used in the derivation of PK parameters.

**Table 2. Plasma Nirmatrelvir and Ritonavir PK Parameters Definitions**

Parameter	Definition	Method of Determination
AUC inf *	Area under the concentration-time curve from time 0 extrapolated to infinity	AUC last + (C last */k el ), where C last * is the predicted plasma concentration at the last quantifiable time point from the log-linear regression analysis
AUC last	Area under the plasma concentration-time curve from time 0 to the time of the last measurable concentration (C last ).	Linear/Log trapezoidal method.
AUC 12	Area under the concentration-time curve from time 0 to 12 hours	Linear/Log trapezoidal method.
C max	Maximum observed concentration	Observed directly from data
T max	Time for C max	Observed directly from data as time of first occurrence
t 1/2 *	Terminal half-life	Log e (2)/k el , where k el is the terminal phase rate constant calculated by a linear regression of the loglinear concentration-time curve. Only those data points judged to describe the terminal loglinear decline will be used in the regression.
CL/F*	Apparent clearance of drug from eg, plasma	Dose/AUC inf
V z /F*	Apparent volume of distribution	Dose/(AUC inf • k el )

\*If data permits.

Additionally, saliva concentration by nominal collection time and by treatment will be provided, if collected and analyzed. The ratio of saliva/plasma concentrations will be listed for each time point saliva is collected.

### 9.3.2. Statistical Methods for PK Data

For the primary objective, natural log transformed AUCinf (if data permits), AUClast and Cmax for nirmatrelvir and ritonavir will be analyzed using a mixed effect model with sequence, period and treatment as fixed effects and participant within sequence as a random effect. Estimates of the adjusted mean differences (Test-Reference) and corresponding 90% confidence intervals will be obtained from the model. The adjusted mean differences and 90% confidence intervals for the differences will be exponentiated to provide estimates of the ratio of adjusted geometric means (Test/Reference) and 90% confidence intervals for the ratios. Treatment A will be the Reference treatment while Treatments B, C, D and E will be the Test treatments.

PK parameters, including plasma AUCinf (if data permits), AUClast, Cmax, and CCI [REDACTED] (if data permits) of nirmatrelvir and ritonavir will be summarized descriptively by treatment. For AUCinf (if data permits), AUClast, and Cmax, a listing of the individual participant ratios (Test/Reference) will be provided. Box and whisker plots for AUCinf (if data permits), AUClast, and Cmax, will be plotted by treatment.

The plasma concentrations of nirmatrelvir and ritonavir will be listed and descriptively summarized by nominal PK sampling time and treatment. Individual participant, as well as mean and median profiles of the plasma concentration time data will be plotted by treatment using actual (for individual) and nominal (for mean and median) times respectively. Mean and median profiles will be presented on both linear and semi-log scales.

Additional specifications about the tables, listings, and figures will be outlined in the SAP.

### **9.3.3. Other Safety Analyses**

All safety analyses will be performed on the safety population.

AEs, ECGs, BP, PR, and safety laboratory data will be reviewed and summarized on an ongoing basis during the study to evaluate the safety of participants. Any clinical laboratory, ECG, BP, and PR abnormalities of potential clinical concern will be described. Safety data will be presented in tabular and/or graphical format and summarized descriptively, where appropriate.

Medical history and PE and neurological examination information, as applicable, collected during the course of the study will be considered source data and will not be required to be reported, unless otherwise noted. However, any untoward findings identified on physical and/or neurological examinations conducted during the active collection period will be captured as AEs, if those findings meet the definition of an AE. Data collected at Screening that are used for inclusion/exclusion criteria, such as laboratory data, ECGs, and vital signs, will be considered source data, and will not be required to be reported, unless otherwise noted. Demographic data collected at Screening will be reported.

### **9.3.4. Other Analyse(s)**

#### **9.3.4.1. Biomarker Assessment**

Biomarker data from Retained Research Samples may be collected as per [SoA](#), during or after the trial and retained for future analyses; the results of such analyses are not planned to be included in the CSR.

## **9.4. Interim Analyses**

No formal interim analysis will be conducted for this study. As this is an open-label study, the sponsor may conduct unblinded reviews of the data during the course of the study for the purpose of safety assessment, facilitating PK/PD modeling, and/or supporting clinical development.

## **9.5. Sample Size Determination**

A sample size of 15 evaluable participants will provide 90% CIs for the difference between treatments of  $\pm 0.1175$  and  $\pm 0.0924$  on the natural log scale for  $AUC_{\text{inf}}$  and  $C_{\text{max}}$  for nirmatrelvir, respectively, with 80% coverage probability.

Parameter	Estimated Effect (100*Test/Reference)	90% CI	CI Width
AUC inf	85%	0.7558, 0.9560	0.2002
	90%	0.8002, 1.0122	0.2119
	95%	0.8447, 1.0684	0.2237
	100%	0.8892, 1.1246	0.2355
	105%	0.9336, 1.1809	0.2473
	110%	0.9781, 1.2371	0.2590
	115%	1.0225, 1.2933	0.2708
C max	85%	0.7750, 0.9323	0.1573
	90%	0.8206, 0.9871	0.1665
	95%	0.8662, 1.0420	0.1758
	100%	0.9117, 1.0968	0.1851
	105%	0.9573, 1.1516	0.1943
	110%	1.0029, 1.2065	0.2036
	115%	1.0485, 1.2613	0.2128

These estimates are based on the assumption that within-participant standard deviations are 0.1752 and 0.1378 for lnAUCinf and lnCmax, respectively, as obtained from clinical Studies C4671008 and C4671014 in healthy participants.

In addition, a sample size of 15 evaluable participants will provide 90% CIs for the difference between treatments of  $\pm 0.1625$  and  $\pm 0.2201$  on the natural log scale for AUCinf and Cmax for ritonavir, respectively, with 80% coverage probability.

Parameter	Estimated Effect (100*Test/Reference)	90% CI	CI Width
AUC inf	85%	0.7225, 1.0000	0.2775
	90%	0.7650, 1.0588	0.2938
	95%	0.8075, 1.1177	0.3102
	100%	0.8500, 1.1765	0.3265
	105%	0.8925, 1.2353	0.3428
	110%	0.9350, 1.2941	0.3591
	115%	0.9775, 1.3530	0.3755
C max	85%	0.6821, 1.0592	0.3771
	90%	0.7222, 1.1215	0.3993
	95%	0.7623, 1.1838	0.4215
	100%	0.8025, 1.2461	0.4437
	105%	0.8426, 1.3085	0.4659
	110%	0.8827, 1.3708	0.4880
	115%	0.9228, 1.4331	0.5102

These estimates are based on the assumption that within-participant standard deviations are 0.2424 and 0.3282 for lnAUCinf and lnCmax, respectively, as obtained from clinical studies C4671008 and C4671014 in healthy participants that used nirmatrelvir/ritonavir commercial tablets.

Participants who withdraw from the study or discontinue treatment, or whose PK samples are considered to be nonevaluable with respect to the primary PK objective may be replaced at the discretion of the investigator upon consultation with the sponsor.

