## Sample Size Determination

Total of 15 participants will be enrolled, so that each treatment sequence will have 3 participants. A sample size of 15 participants will be sufficient to provide a reliable estimate of rBA and intrasubject variability of nirmatrelvir and ritonavir. Participants who withdraw from the study or discontinue treatment, or whose PK samples are considered to be nonevaluable with respect to the primary PK objective may be replaced at the discretion of the investigator upon consultation with the sponsor.

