## 4. STUDY DESIGN

### 4.1. Overall Design

This is a Phase 1, open-label, single-dose, randomized, crossover study in healthy adult participants to estimate rBA of 4 different nirmatrelvir/ritonavir 300/100 mg FDC tablets formulations (Test formulations) compared to the nirmatrelvir/ritonavir 300/100 mg commercial tablet formulation (Reference formulation) under fasted conditions. The study will also assess the safety and tolerability, of nirmatrelvir/ritonavir FDC and commercial tablet formulations in healthy adult participants. CCI [REDACTED]

Approximately 15 healthy male and/or female participants will be enrolled and randomized to 1 of 5 possible treatment sequences to ensure at least 12 participants will complete the study. Participants who discontinue from the study for non-safety reasons may be replaced at the sponsor's discretion in collaboration with the investigator. The replacement participant will receive the same treatment sequences as the participant who discontinued.

The study will consist of 5 treatments. Each enrolled participant will participate in 4 study periods to receive 4 different treatments according to the sequence determined by randomization:

- Treatment A: Single oral dose of nirmatrelvir/ritonavir 300 (2 × 150 )/100 mg commercial tablets under fasted conditions (Reference)

- Treatment B: Single oral dose of nirmatrelvir/ritonavir 300/100 mg (2 × 150/50 mg) FDC tablets Test formulation 1 (low disintegrant) under fasted conditions (Test 1)
- Treatment C: Single oral dose of nirmatrelvir/ritonavir 300/100 mg (2 × 150/50 mg) FDC tablets Test formulation 2 (high disintegrant) under fasted conditions (Test 2)
- Treatment D: Single oral dose of nirmatrelvir/ritonavir 300/100 mg (2 × 150/50 mg) FDC tablets Test formulation 3 (high drug loading) under fasted conditions (Test 3)
- Treatment E: Single oral dose of nirmatrelvir/ritonavir 300/100 mg (3 × 100/33.3 mg) FDC tablets Test formulation 4 under fasted conditions (Test 4)

Participants will be randomly assigned to 1 of 5 sequences as shown below in Table 1. Participants will be discharged on Day 4 of Period 4, following completion of all assessments. Between each treatment, a minimum of 4 days washout is proposed to minimize any residual nirmatrelvir and ritonavir concentrations prior to start of the next treatment. The total planned duration of participation from the Screening visit to the last follow-up phone call, is approximately 12 weeks.

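### The 90% CI half-widths in Protocol 9.5 are about 13% too narrow: the standard error counts 15 participants per treatment, but each participant receives only four of the five treatments

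*Protocol*

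**What the plan says.** Protocol 9.5 opens its precision statement with the words "A sample size of 15 evaluable participants will provide 90% CIs for the difference between treatments of". The nirmatrelvir half-widths it then gives, in log units, are 0.1175 for AUCinf and 0.0924 for Cmax, "with 80% coverage probability". The corresponding ritonavir figures are ±0.1625 and ±0.2201. Two tables carry these half-widths to ratios from 85% to 115%, which makes 28 intervals. The inputs are "within-participant standard deviations are 0.1752 and 0.1378 for" nirmatrelvir lnAUCinf and lnCmax, and "within-participant standard deviations are 0.2424 and 0.3282 for" the same two ritonavir parameters.

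On the design, Protocol 4.1 says: "Each enrolled participant will participate in 4 study periods to receive 4 different treatments according to the sequence determined by randomization". Table 1 lists five sequences of three participants, each omitting one treatment. The study is "randomized to 1 of 5 possible treatment sequences to ensure at least 12 participants will complete the study".

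On the analysis, Protocol 9.3.2 and SAP 8.2 specify a mixed model with sequence, period and treatment fixed and participant within sequence random. "Estimates of the adjusted mean differences (Test-Reference) and corresponding 90% confidence intervals will be obtained from the model". The SAS code in SAP Appendix 1 matches this and uses Kenward-Roger degrees of freedom.

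The Synopsis concludes: "A sample size of 15 participants will be sufficient to provide a reliable estimate of rBA and intrasubject variability of nirmatrelvir and ritonavir".

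**The concern.** Fifteen is the total number of participants, not the number who receive any one treatment. Each sequence leaves out one treatment, and Sequence 2 never receives the Reference. A half-width built on 15 participants per comparison therefore credits the study with data it will not collect.

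The study tests no hypothesis and has no decision rule (Protocol 9.1, SAP 4.1 and 4.2). Expected precision is what the reader is given for judging whether 15 participants are enough. If it is overstated, that judgement rests on wrong figures for all four parameters and all 28 tabulated intervals.

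**Working it through.** **Inputs.** N = 15, 90% two-sided CI, 80% probability of meeting the half-width, and SDs of 0.1752, 0.1378, 0.2424 and 0.3282 (Protocol 9.5). Three participants in each of five four-period sequences (Table 1). Model from Protocol 9.3.2 and SAP Appendix 1.

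**Step 1: reproduce the stated figures.** Section 9.5 gives no formula. The usual one is

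half-width = t(0.95, df) × SD × √(2/n) × √(χ²(0.80, df)/df).

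- df = 60 observations − 15 participants − 3 periods − 4 treatments = 38.
- t(0.95, 38) = 1.6860; χ²(0.80, 38) = 45.076; √(45.076/38) = 1.0891.
- With n = 15, √(2/15) = 0.36515, and the multiplier is 1.6860 × 0.36515 × 1.0891 = 0.6705.

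Multiplying by the four SDs gives 0.1175, 0.0924, 0.1625 and 0.2201, which match the protocol to four decimals. In a grid of n between 9 and 20 and df from 5 to 79, n = 15 with df = 38 was the only match at the stated 80%. The 38 df come from the real four-period design (a complete five-period design would have 52). Only the variance term treats all 15 participants as receiving both treatments.

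**Step 2: the variance under Table 1.** The table is a balanced incomplete block design:

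- 5 treatments, 4 per participant;
- each treatment appears in 4 of 5 sequences: 4 × 3 = 12 participants;
- each Test/Reference pair appears in 3 of 5 sequences: 3 × 3 = 9 participants;
- each treatment occurs equally often in each period, so the period adjustment costs nothing further.

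Efficiency factor = (9 × 5)/(12 × 4) = 45/48 = 0.9375. Effective n = 12 × 0.9375 = 11.25. Hence

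Var(Test − A) = 2·SD²/11.25 = 0.1778·SD², against 2·SD²/15 = 0.1333·SD² in the protocol.

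Least squares on the 60-row design matrix gives 0.17778·SD² for all four contrasts, with 38 residual df. Generalised least squares under the planned model gives the same value whatever the between-participant variance. Sequence is a fixed effect and everyone in a sequence receives the same four treatments, so there is no between-participant treatment information to recover.

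**Step 3: corrected half-widths.** √(2/11.25) = 0.42164, and the multiplier is 1.6860 × 0.42164 × 1.0891 = 0.7742. The ratio to the protocol's multiplier is √(15/11.25) = 1.1547.

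| Parameter | SD | Stated | Corrected | Stated CI at ratio 100% | Corrected CI at ratio 100% |
|---|---|---|---|---|---|
| Nirmatrelvir AUCinf | 0.1752 | 0.1175 | 0.1356 | 0.8892–1.1246 | 0.8732–1.1453 |
| Nirmatrelvir Cmax | 0.1378 | 0.0924 | 0.1067 | 0.9117–1.0968 | 0.8988–1.1126 |
| Ritonavir AUCinf | 0.2424 | 0.1625 | 0.1877 | 0.8500–1.1765 | 0.8289–1.2064 |
| Ritonavir Cmax | 0.3282 | 0.2201 | 0.2541 | 0.8025–1.2461 | 0.7756–1.2893 |

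**Step 4: probability of achieving the stated half-width.** This is P(χ²₃₈ ≤ 38 × (stated/(t × SD × 0.42164))²). For nirmatrelvir AUCinf, t × SD × 0.42164 = 0.12454, so the bound is 38 × (0.1175/0.12454)² ≈ 33.8 and the probability is 0.337. The other three parameters give 0.336 to 0.337. A simulation for nirmatrelvir AUCinf gave 0.338.

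**Step 5: 12 completers.** Averaged over all 455 ways of losing 3 of 15 participants:

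| Data from the three who leave | df | Half-width relative to stated | Probability of meeting stated |
|---|---|---|---|
| None, or one period only | 29 | 33% wider | about 11% |
| Two periods | 32 | 27% wider | about 16% |
| Three periods | 35 | 21% wider | about 24% |

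In the first row the half-widths are about 0.156, 0.123, 0.216 and 0.293.

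**The case against.** The case on the other side is about consequence, since the variance itself is not in dispute.

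- **Nothing formal depends on these figures.** There is no equivalence bound, target width or go/no-go threshold. The final model works from the data actually collected, so the reported intervals will be right. This stands, and it confines the error to the planning text.
- **Precision is not the only aim.** The Synopsis also cites a reliable estimate of intrasubject variability. That depends on the residual df, which are correct at 38. This stands too.
- **The formula is inferred.** Section 9.5 does not print one. However, one formula reproduces all four values to four decimals, and no entry elsewhere in the documents supplies a different basis. The corrected variance does not depend on the inference, because it comes from Table 1 and the planned model.
- **The word coverage can mislead.** In Section 9.5 it means the chance that the half-width is no larger than stated. The 34% refers to that chance; the 90% CIs do not under-cover.
- **The 12-completer figures depend on what dropouts contribute.** The PK parameter set keeps anyone with at least one primary parameter, and replacement into the same sequence is allowed. The 33% figure is therefore the pessimistic end of a 21% to 33% range. Section 9.5 is also expressly conditional on 15 evaluable participants, so this scenario is a useful addition rather than part of the error.

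None of these points restores the stated half-widths.

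**Conclusion.** The point holds. With 15 evaluable participants and the protocol's own SDs, the design delivers half-widths about 15.5% wider than Section 9.5 states; equivalently, the stated values are about 13% too narrow. The chance of achieving them is about 34%, not 80%. All four parameters and all 28 tabulated intervals are affected.

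The result rests on Table 1 as written, complete four-period data from all 15 participants, the planned model with sequence fixed, and the stated SDs. It does not depend on the between-participant variance. Any loss of participants without replacement makes the gap larger. Fifteen participants may still be adequate for an estimation study, but that should be judged on the corrected figures.

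**What to change.** In Protocol 9.5:

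1. Replace the half-widths with 0.1356 and 0.1067 (nirmatrelvir AUCinf, Cmax) and 0.1877 and 0.2541 (ritonavir AUCinf, Cmax).
2. Regenerate both tables from a variance of 2·SD²/11.25 with 38 df, and state the formula.
3. Say that each treatment is received by 12 participants and each Test/Reference pair by 9.
4. Describe the 80% as the probability that the half-width does not exceed the stated value.
5. Preferably, add the precision at the planned minimum of 12 completers, with the assumption made about dropouts' data.

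The cost is protocol wording and table entries, and a less favourable stated precision. N, the sequences and the analysis model can stay as they are. For scale, reaching the precision now stated would take 20 participants under this design (four per sequence, 53 df), where the multiplier is 0.658 × SD against the protocol's 0.6705 × SD.

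### The CI precision in Section 9.5 assumes 15 evaluable participants, but the plan secures only 12 completers and gives no precision for that number

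*Protocol*

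**What the plan says.** Section 9.5 of the protocol justifies the sample size by precision alone: "A sample size of 15 evaluable participants will provide 90% CIs for the difference between treatments of" ±0.1175 (AUCinf) and ±0.0924 (Cmax) on the natural log scale for nirmatrelvir, "with 80% coverage probability". A parallel sentence gives ±0.1625 and ±0.2201 for ritonavir. The inputs are that "within-participant standard deviations are 0.1752 and 0.1378" for nirmatrelvir and "within-participant standard deviations are 0.2424 and 0.3282" for ritonavir (lnAUCinf and lnCmax in each case).

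The synopsis uses the same number for enrolment: "Total of 15 participants will be enrolled, so that each treatment sequence will have 3 participants". Section 4.1 describes it differently. About 15 participants are "enrolled and randomized to 1 of 5 possible treatment sequences to ensure at least 12 participants will complete the study". The synopsis (Number of Participants) and SAP Section 2.1 repeat this.

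Replacement is discretionary wherever it appears, and its scope varies. Section 4.1, the synopsis under Overall Design and SAP 2.1 mention it for participants who discontinue for non-safety reasons. Section 9.5 and the synopsis under Sample Size Determination extend it to any withdrawal, any treatment discontinuation and nonevaluable PK samples.

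**The concern.** The number enrolled is used as the number evaluable. The plan tolerates losing 3 of 15 participants, but the precision calculation allows for no unreplaced loss, and no section gives the precision at 12.

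This matters because the study has no statistical hypotheses (Protocol 9.1) and no decision rules (SAP 4.2). The expected width of the 90% confidence intervals is the only quantitative justification for the sample size. If it holds only at a number that the plan does not secure, the reader is given a more favourable picture of the four formulation comparisons than the plan supports.

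**Working it through.** **Inputs.** SDs of 0.1752, 0.1378, 0.2424 and 0.3282 (Section 9.5); two-sided 90% intervals (Section 9.3.2); 80% probability of achieving the width (Section 9.5); four periods, five treatments and three participants per sequence (Table 1).

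**Step 1: reproduce the stated figures.** The protocol does not print its formula. The following one returns all four values to four decimals:

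half-width = SD × √(2/n) × t(0.95, df) × √(χ²(0.80, df)/df)

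Here n = 15 and df = 60 − 15 − 3 − 4 = 38 (observations less participants, periods and treatments). With t = 1.6860 and √(45.08/38) = 1.0891, nirmatrelvir AUCinf is 0.1752 × √(2/15) × 1.6860 × 1.0891 = 0.1175. The others come to 0.0924, 0.1625 and 0.2201.

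**Step 2: same formula, 12 fully evaluable.** df = 48 − 12 − 3 − 4 = 29, t = 1.6991 and √(35.14/29) = 1.1008. Nirmatrelvir AUCinf is 0.1752 × √(2/12) × 1.6991 × 1.1008 = 0.1338, and 0.1338/0.1175 = 1.139. The chance of a half-width no larger than 0.1175 is P(χ² with 29 df ≤ 27.1) = 0.43. Smaller losses also exceed the stated value: 0.1222 at n = 14 (+4%) and 0.1276 at n = 13 (+9%).

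**Step 3: the design in Table 1.** The factor 2/n assumes that every participant receives both treatments being compared. In Table 1 each participant receives four of the five, so among 15 participants each treatment is taken by 12 and each Test–Reference pair occurs within only 9. Each treatment appears once in every period across the five sequences, so periods are balanced. The contrast variance is therefore 2 × 4/(9 × 5) = 8/45 = 0.1778 times SD², not 2/15 = 0.1333. A least-squares fit of the layout gives the same value. The half-widths increase by √(0.1778/0.1333) = 1.155. With no loss at all, the chance of meeting the stated width is about 34%.

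**Step 4: Table 1 with all data lost from three participants.** Over all 455 choices of 3 from 15, least squares on participant, period and treatment gives a variance factor averaging 0.228 (range 0.202 to 0.267), with 29 df.

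| Half-width (ln scale) | Nirmatrelvir AUCinf | Nirmatrelvir Cmax | Ritonavir AUCinf | Ritonavir Cmax |
|---|---|---|---|---|
| Stated, n = 15 | 0.1175 | 0.0924 | 0.1625 | 0.2201 |
| Protocol formula, n = 12 | 0.1338 | 0.1052 | 0.1851 | 0.2506 |
| Table 1 design, 15 complete | 0.1356 | 0.1067 | 0.1877 | 0.2541 |
| Table 1 design, 12 (average) | 0.156 | 0.123 | 0.216 | 0.293 |

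The last row is about 33% above the stated values. For nirmatrelvir AUCinf it ranges from 0.147 to 0.169, depending on which participants are lost.

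**On the ratio scale.** For ritonavir Cmax at an estimated ratio of 100%, Section 9.5 gives 0.8025 to 1.2461. The protocol formula at 12 gives 0.778 to 1.285. Table 1 with 15 complete gives exp(±0.2541) = 0.776 to 1.289, and the Table 1 average at 12 gives exp(±0.293) = 0.746 to 1.340.

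**The case against.** The strongest reply is that Section 9.5 is conditional. It states what 15 evaluable participants would provide, and its arithmetic reproduces exactly under its own formula. That stands. The fault lies in the number and design to which the formula is applied, not in the calculation.

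Four stronger readings are tempting, and the documents do not support them.

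- **That the stated precision would be met if nobody dropped out.** It would not. With 15 full completers the Table 1 design gives 0.1356 for nirmatrelvir AUCinf, already wider than the 0.1338 from the protocol's formula at n = 12. Attrition is one of two separate causes.
- **That 12 completers means 12 evaluable participants.** Section 4.4 requires a completer to finish the last scheduled procedure, which is the follow-up contact. Someone missed at that contact is a non-completer with full PK data. The PK parameter set in Section 9.2 keeps anyone with at least one primary parameter, so partial data stay in the model. If the three leave after Period 3, the average Table 1 half-width for nirmatrelvir AUCinf is 0.142; after Period 2 it is 0.149. Conversely, SAP 5.7 and 7.3 allow PK data from completers to be excluded.
- **That nothing can restore 15.** Replacement can, and Section 4.1 gives the replacement the same sequence. But it is optional, so it does not secure 15. Participants are also confined throughout, and 12 is a floor rather than a forecast.
- **That the study is underpowered or its error rates are affected.** There is no test and no decision rule, and the observed intervals will be reported whatever was planned.

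**Conclusion.** The point holds as a mismatch between the stated precision and what the plan secures. Under the protocol's own formula, the half-widths at 12 fully evaluable participants are 13.9% wider than stated (equivalently, the stated ones are 12.2% narrower, since 0.1175/0.1338 = 0.878), and the 80% assurance falls to 43%. In the Table 1 design the half-widths are about 15% wider than stated with no loss, and about 33% wider on average if three participants contribute no data.

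These figures rest on the protocol's SDs and on a formula inferred from an exact match to four values. The 12-participant Table 1 figures are the planned-minimum case with all data lost from three people; partial data would narrow them somewhat. Participant effects were treated as fixed. With complete data this loses nothing, because the model's sequence effect already absorbs the between-participant treatment information.

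The consequence is confined to the stated precision, so this should be corrected, but it does not threaten the validity of the analysis.

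**What to change.** In Section 9.5, regenerate both CI tables with the contrast variance of the Table 1 design, for two cases: 15 participants with no unreplaced loss, and 12 as the planned minimum. State what is assumed about partial data at 12. Rerunning the existing formula at n = 12 would not be enough, because its 0.1338 is still narrower than the no-loss value of 0.1356.

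Have the synopsis sample-size statement cite the new figures. Keep 15 as the enrolment target. Reconcile the replacement wording between Section 4.1 (non-safety discontinuations) and Section 9.5 (any withdrawal, discontinuation or nonevaluable PK), with matching text in the synopsis and SAP 2.1.

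The cost is two tables and a few sentences. No extra participants are needed and the analysis model does not change, but the stated precision becomes less favourable.
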